### 1.5 Secondary endpoint for replication (assay sensitivity) and RCT finding

Major bleeding; RR= 0.31 (95% CI 0.17–0.55)

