### 6.3 Outcome variables and study follow-up:

#### 6.3.1 Outcome variables

Primary Effectiveness outcomes of interest: (definitions provided in **Appendix A**):

- **Primary Outcome:** VTE and cause-specific mortality
- **Secondary Outcome:** Individual components
  - Hospital admission for VTE (principal diagnosis position)
  - Cause-specific mortality
    - Inpatient mortality identified using discharge status codes from hospitalization for VTE

Safety outcome of interest:

1. Major bleeding

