|                                                             | 
Measured 180 days prior to and including day of drug initiation in any diagnosis position and in an inpatient care setting
 
Gastrointestinal bleeding:
 
ICD-9 Dx:
531.0x gastric ulcer w/ hemorrhage,
531.2x gastric ulcer w/ hemorrhage and perforation
531.4x
531.6x chronic / unspecified ulcer w/ hemorrhage
532.0x, 532.2x, 532.4x, 532.6x, 533.0x, 533.2x, 533.4x, 533.6x,
534.0x, 534.2x, 534.4x, 534.6x, 562.0x, 562.1x, 568.8x, 569.3x, 569.8x
578.x Gastrointestinal hemorrhage
 
ICD-10 Dx:
K25.0x, K25.2x, K25.6x, K26.0x, K26.2x, K26.4x, K26.6x, K27.0x, K27.2x, K27.4x, K27.6x,
K28.0x, K28.2x, K28.4x, K28.6x, K55.21, K57.xx, K62.5x, K63.1x, K63.81, K66.1x, K92.0x,
K92.1x, K92.2x
 
ICD-9 Px: 44.43
ICD-10 Px: 0W3PBZZ
 |  |  |
| • 2 months                                                  |                                                                                                                                                                                                                                                                                                                                                                                                                                                                                                                                                                                                                                                                                                                                                                                                                            |  |  |

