| - Gross hematuria                                           | 
Measured 1 day prior to and including the day of drug initiation in any diagnosis position in an inpatient or outpatient care setting
 
Gross hematuria:
 
ICD-9 Dx: 599.71 (not 599.7x)
ICD-10 Dx: R31.0
                                                                                                                                                                                                                                                                                                                                                                                                                                                                                                                                                                                      |  |  |
| - Evidence of poor healing of a major wound or major trauma | 
Measured 1 day prior and including the day of drug initiation in any diagnosis position in an inpatient or outpatient care setting
 
Non-healing surgical wound
 
ICD-9 Dx: 998.33
ICD-10 Dx: T81.33XA
                                                                                                                                                                                                                                                                                                                                                                                                                                                                                                                                                                                         |  |  |

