| 
- Intracranial neoplasm, arteriovenous malformation or aneurysm
                                                                                                                                                                                                                                                                                                                                                                                  | 
Measured 1 day prior to and including the day of drug initiation in any diagnosis position and in an inpatient or outpatient care setting
 
Intracranial neoplasm:
ICD-9 Dx: 239.6x, 191.xx, 225.xx
ICD-10 Dx: D49.6x, C71.x, D33.0x, D33.1x, D33.2x
 
AV malformation of brain:
ICD-9 Dx: 747.81
ICD-10 Dx: Q28.2x, Q28.3x
 
Cerebral aneurysm
ICD-9 Dx: 437.3x
ICD-10 Dx: I67.1x
 |  |  |
| 
- Overt major bleeding
                                                                                                                                                                                                                                                                                                                                                                                                                           | 
Measured 1 day prior and including the day of drug initiation in any diagnosis position and in an inpatient or outpatient care setting
 
See 'Major Bleeding' sheet for codes
                                                                                                                                                                                                                                                             |  |  |

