# Appendix A

| Title          |                                                                                           |
|----------------|-------------------------------------------------------------------------------------------|
| Major Bleeding |                                                                                           |
| ICD-9 Dx       |                                                                                           |
| 423            | HEMOPERICARDIUM                                                                           |
| 430            | SUBARACHNOID HEMORRHAGE                                                                   |
| 431            | INTRACEREBRAL HEMORRHAGE                                                                  |
| 432            | NONTRAUMATIC EXTRADURAL HEMORRHAGE                                                        |
| 432.1          | SUBDURAL HEMORRHAGE                                                                       |
| 432.9          | UNSPECIFIED INTRACRANIAL HEMORRHAGE                                                       |
| 459            | HEMORRHAGE UNSPECIFIED                                                                    |
| 531            | ACUTE GASTRIC ULCER WITH HEMORRHAGE                                                       |
| 531            | ACUTE GASTRIC ULCER WITH HEMORRHAGE WITHOUT OBSTRUCTION                                   |
| 531.01         | ACUTE GASTRIC ULCER WITH HEMORRHAGE WITH OBSTRUCTION                                      |
| 531.2          | ACUTE GASTRIC ULCER WITH HEMORRHAGE AND PERFORATION                                       |
| 531.2          | ACUTE GASTRIC ULCER WITH HEMORRHAGE AND PERFORATION WITHOUT OBSTRUCTION                   |
| 531.21         | ACUTE GASTRIC ULCER WITH HEMORRHAGE AND PERFORATION WITH OBSTRUCTION                      |
| 531.4          | CHRONIC OR UNSPECIFIED GASTRIC ULCER WITH HEMORRHAGE                                      |
| 531.4          | CHRONIC OR UNSPECIFIED GASTRIC ULCER WITH HEMORRHAGE WITHOUT OBSTRUCTION                  |
| 531.41         | CHRONIC OR UNSPECIFIED GASTRIC ULCER WITH HEMORRHAGE WITH OBSTRUCTION                     |
| 531.6          | CHRONIC OR UNSPECIFIED GASTRIC ULCER WITH HEMORRHAGE AND PERFORATION                      |
| 531.6          | CHRONIC OR UNSPECIFIED GASTRIC ULCER WITH HEMORRHAGE AND PERFORATION WITHOUT OBSTRUCTION  |

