## Appendix A

|                        |                                                                                          |
|------------------------|------------------------------------------------------------------------------------------|
| M25.072                | Hemarthrosis, left ankle                                                                 |
| M25.073                | Hemarthrosis, unspecified ankle                                                          |
| M25.074                | Hemarthrosis, right foot                                                                 |
| M25.075                | Hemarthrosis, left foot                                                                  |
| M25.076                | Hemarthrosis, unspecified foot                                                           |
| M25.08                 | Hemarthrosis, other specified site                                                       |
| R58                    | Hemorrhage, not elsewhere classified                                                     |
| R31.9                  | Heaturia, unspecified in inpatient confinement                                           |
| R31.9                  | Heaturia, unspecified in inpatient confinement                                           |
| R04.2                  | Hemoptysis                                                                               |
| R04.9                  | Hemorrhage from respiratory passages, unspecified                                        |
| R04.81                 | Acute idiopathic pulmonary hemorrhage in infants                                         |
| R04.89                 | Hemorrhage from other sites in respiratory passages                                      |
| R31.0                  | Gross hematuria                                                                          |
| R31.1                  | Benign essential microscopic hematuria                                                   |
| R31.2                  | Other microscopic hematuria                                                              |
|                        |                                                                                          |
| ICD-9 and 10 Px |                                                                                          |
| 0W.3P8ZZ               | Control Bleeding in Gastrointestinal Tract, Via Natural or Artificial Opening Endoscopic |

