| 453.2                                      | EMBOLISM AND THROMBOSIS OF INFERIOR VENA CAVA                                         |
| 453.4                                      | ACUTE VENOUS EMBOLISM AND THROMBOSIS OF DEEP VESSELS OF LOWER EXTREMITY               |
| 453.4                                      | ACUTE VENOUS EMBOLISM AND THROMBOSIS OF UNSPECIFIED DEEP VESSELS OF LOWER EXTREMITY   |
| 453.41                                     | ACUTE VENOUS EMBOLISM AND THROMBOSIS OF DEEP VESSELS OF PROXIMAL LOWER EXTREMITY      |
| 453.42                                     | ACUTE VENOUS EMBOLISM AND THROMBOSIS OF DEEP VESSELS OF DISTAL LOWER EXTREMITY        |
| 453.5                                      | CHRONIC VENOUS EMBOLISM AND THROMBOSIS OF DEEP VESSELS OF LOWER EXTREMITY             |
| 453.5                                      | CHRONIC VENOUS EMBOLISM AND THROMBOSIS OF UNSPECIFIED DEEP VESSELS OF LOWER EXTREMITY |
| 453.51                                     | CHRONIC VENOUS EMBOLISM AND THROMBOSIS OF DEEP VESSELS OF PROXIMAL LOWER EXTREMITY    |
| 453.52                                     | CHRONIC VENOUS EMBOLISM AND THROMBOSIS OF DEEP VESSELS OF DISTAL LOWER EXTREMITY      |
| 453.8                                      | ACUTE VENOUS EMBOLISM AND THROMBOSIS OF OTHER SPECIFIED VEINS                         |
| 453.82                                     | ACUTE VENOUS EMBOLISM AND THROMBOSIS OF DEEP VEINS OF UPPER EXTREMITY                 |
| 453.83                                     | ACUTE VENOUS EMBOLISM AND THROMBOSIS OF UPPER EXTREMITY UNSPECIFIED                   |
| 453.84                                     | ACUTE VENOUS EMBOLISM AND THROMBOSIS OF AXILLARY VEINS                                |
| 453.85                                     | ACUTE VENOUS EMBOLISM AND THROMBOSIS OF SUBCLAVIAN VEINS                              |
| 453.86                                     | ACUTE VENOUS EMBOLISM AND THROMBOSIS OF INTERNAL JUGULAR VEINS                        |
| 453.87                                     | ACUTE VENOUS EMBOLISM AND THROMBOSIS OF OTHER THORACIC VEINS                          |
| 453.89                                     | ACUTE VENOUS EMBOLISM AND THROMBOSIS OF OTHER SPECIFIED VEINS                         |

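### As printed, the Major Bleeding list counts urinary and respiratory bleeding under ICD-10 but not under ICD-9, so the endpoint changes with coding era

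*Combined protocol and SAP*

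**What the plan says.** Section 6.3.1 lists major bleeding under "Safety outcome of interest", and Section 1.5 gives it the assay-sensitivity role with the trial benchmark "Major bleeding; RR= 0.31 (95% CI 0.17–0.55". The only printed definition is the Major Bleeding sheet in Appendix A. That sheet is used a second time: the overt-bleeding exclusion, assessed on the day of initiation and the day before, carries the instruction "See 'Major Bleeding' sheet for codes".

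The ICD-10 half of the sheet includes hematuria (R31.0, R31.1, R31.2, R31.9) and respiratory bleeding (R04.2, R04.81, R04.89, R04.9); R04.89 is labelled "Hemorrhage from other sites in respiratory passages". The ICD-9 half runs from 423 to 719.19 and has neither group. The separate gross-hematuria exclusion in Appendix A does print an ICD-9 code: "ICD-9 Dx: 599.71 (not 599.7x".

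Two further places matter. The ICD-9 half prints 531 on two rows, one of them labelled "ACUTE GASTRIC ULCER WITH HEMORRHAGE WITHOUT OBSTRUCTION", where the gastrointestinal-bleeding exclusion writes "531.0x gastric ulcer w/ hemorrhage". On the VTE outcome sheet, ICD-9 453.2 is "EMBOLISM AND THROMBOSIS OF INFERIOR VENA CAVA".

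Section 5.2.1 opens cohort entry on 21 August 2014 in every database. Appendix A says that ICD-9 codes were converted to ICD-10 by forward and backward mapping, and refers to an outside folder for full lists and anything missing.

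**The concern.** Both coding systems are printed because follow-up spans both. If the lists are applied as written, a hematuria or hemoptysis claim is a major bleed under ICD-10, while the same event under ICD-9 is not. The mapping statement suggests that the halves were meant to correspond, and the ICD-9 gross-hematuria code was at hand, so the gap does not look deliberate.

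At stake is the endpoint meant to show that the database study can recover a known trial result. If its content shifts part-way through the study, a departure from the benchmark is harder to interpret. If the arms are also spread differently over calendar time, the shift becomes a difference between arms. Section 6.2 says that the full covariate list is in Table 1 of Appendix B, and that table has no index-date or index-year row.

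**Working it through.** The plan states no figure on this point, so the check compares the printed lists and then measures exposure to the ICD-9 era.

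**1. Row count, Major Bleeding sheet**

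| | ICD-9 half | ICD-10 half |
|---|---|---|
| Urinary rows | 0 | 5 (4 distinct; R31.9 is printed twice) |
| Respiratory rows | 0 | 4 |

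The ICD-9 half has 78 printed rows and 61 distinct codes. They cover pericardial, intracranial, unspecified, gastrointestinal, peritoneal and joint bleeding.

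**2. Share of the entry window under ICD-9.** Start: 21 August 2014 (Section 5.2.1). Switch: 1 October 2015, assumed. Days before the switch: 133 in 2014 + 273 in 2015 = 406.

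- Medicare, to 31 December 2017: 406 / 1,229 = 33%
- MarketScan, to 31 December 2018: 406 / 1,594 = 25%
- Optum, to 31 March 2020: 406 / 2,050 = 20%

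Moving the assumed switch by 30 days changes these by 30/1,229 = 2.4, 30/1,594 = 1.9 and 30/2,050 = 1.5 percentage points. They are shares of calendar days, not of patients or follow-up.

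**3. When this would distort the comparison.** Let w and a be the ICD-9 shares of warfarin and apixaban follow-up. Let x be the proportional addition to captured bleeds from the ICD-10-only codes, taken as equal in the arms. Relative to a list that counts these codes throughout, or one that never does, the apixaban-to-warfarin ratio is multiplied by

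(1 + (1 − a)x) / (1 + (1 − w)x).

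This equals 1 when a = w. The documents give none of w, a or x, so no value follows.

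**4. Eligibility.** The gross-hematuria exclusion has the same one-day window and care settings as the overt-bleeding exclusion and lists both 599.71 and R31.0. Gross hematuria is therefore excluded in both eras. R31.1, R31.2, R31.9 and the R04 codes exclude only under ICD-10. The flowchart step that contains overt bleeding, together with six other criteria, removed 57 + 33 + 111 = 201 of 4,588 + 6,633 + 9,015 = 20,236 patients (1.0%). This suggests a small effect but does not bound it.

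**5. Missing digits.** Fourteen ICD-9 rows have no decimal.

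| Printed on the bleeding sheet | Printed elsewhere in Appendix A |
|---|---|
| 531, 532, 533, 534 (two rows each) | 531.0x, 532.0x, 533.0x, 534.0x (gastrointestinal bleeding) |
| 459 | 459.0x (intraocular bleeding) |
| 423 | none; only its hemopericardium label points to a subcode |
| 430, 431, 432, 578 | whole categories used as bleeding (430.xx, 431.xx, 432.xx, 578.x) |

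The first three lines are the ones in question: six codes on ten rows. Twelve other ulcer codes and 719.1 appear twice under different labels, which fits dropped trailing zeros. The Pregnancy sheet keeps 72.0, 73.0 and 74.0, so PDF extraction is an unlikely cause.

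**6. VTE sheet.** After I82.1 the ICD-10 list repeats I80.3 and goes on to I82.4. No entry names the vena cava.

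**The case against.** The strongest reply is that the printed sheet may not be what was run. Every shortened row keeps a label naming the intended hemorrhage code, duplicated parent and child numbers look like spreadsheet display, and the appendix sends the reader to an outside folder. This stands for the missing digits: they are a reason to check the executed list, not evidence of a wrong extraction. It is weaker for the urinary and respiratory rows, where no label or placeholder shows that ICD-9 codes were intended.

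A setting or position rule could also make the extra ICD-10 codes rare. The VTE sheet states such a rule (inpatient, primary position). The bleeding sheet states none, apart from an inpatient note on R31.9.

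A reader might infer bias against apixaban: the window opens when apixaban became available for this indication, so warfarin starters may enter earlier and have more bleeds go uncounted. The documents do not support this. They give no entry dates by arm. The nearest matched figure in Appendix B, mean prior days in the database, is slightly longer for warfarin in all three sources (1,631 against 1,568; 2,204 against 2,093; 720 against 682). It is a weak proxy, but it does not show earlier warfarin entry. Moreover, if 531 or 459 were matched as a prefix, non-bleeding claims would be added in the ICD-9 era, which pushes the other way. Any numerical multiplier would rest on an invented era split.

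The bleeding list does not define the primary VTE outcome, and the Section 10 power tables do not use it.

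**Conclusion.** The two halves of the Major Bleeding sheet, as printed, define different endpoints: eight distinct urinary and respiratory codes count under ICD-10 and none under ICD-9. Under the assumed switch date, a fifth to a third of each entry window falls in the era with the narrower definition. The outcome, and to a lesser degree the overt-bleeding exclusion, therefore change with calendar time, and no index-date covariate is listed to absorb this.

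The finding is one of inconsistent definition, not of demonstrated bias. With equal era shares in the arms, the result is a mixed endpoint and no between-arm distortion.

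The secondary points are narrower. The digit that identifies hemorrhage is missing for 459 and 531–534, and probably for 423. A reader might add 432 and 578, which also lost a digit, but Appendix A elsewhere treats those whole categories as bleeding. The vena cava mismatch is a single ICD-9 code on a different endpoint and adds nothing to the bleeding point. What was actually executed cannot be judged from the documents.

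**What to change.** Before the comparative analyses in Section 13, which is still blank:

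- Match the bleeding lists concept for concept. Either add ICD-9 urinary and respiratory codes (599.71 is already printed; the rest would have to come from the mapping that the appendix describes), or remove R31.x and R04.x. Which to choose is an endpoint decision for the sponsor; either removes the era difference.
- On the VTE sheet, add the ICD-10 vena cava codes or remove 453.2.
- Store ICD-9 codes as full-length text (459.0x, 531.0x–534.0x) and settle 423 from its label. State whether matching is exact or by prefix: exact matching on 531 can miss the intended bleeds, and prefix matching takes in ulcers without hemorrhage.
- State the diagnosis position and care setting for the bleeding outcome.
- Confirm that the executed lists agree with the printed ones, then re-extract the outcomes and the overt-bleeding exclusion. Section 12 has this document uploaded at registration, so the printed list should stand on its own.

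The cost is an edit to two code lists and a re-run, with no new data. The bleeding count, and possibly the VTE count, will change by an amount that the documents do not let us estimate. A change to the exclusion would also mean repeating the matching and the balance tables.

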| K27.0  | Acute peptic ulcer, site unspecified, with hemorrhage                                       |
| K27.2  | Acute peptic ulcer, site unspecified, with both hemorrhage and perforation                  |
| K27.4  | Chronic or unspecified peptic ulcer, site unspecified, with hemorrhage                      |
| K27.6  | Chronic or unspecified peptic ulcer, site unspecified, with both hemorrhage and perforation |
| K28.0  | Acute gastrojejunal ulcer with hemorrhage                                                   |
| K28.2  | Acute gastrojejunal ulcer with both hemorrhage and perforation                              |
| K28.4  | Chronic or unspecified gastrojejunal ulcer with hemorrhage                                  |
| K28.6  | Chronic or unspecified gastrojejunal ulcer with both hemorrhage and perforation             |
| K55.21 | Angiodysplasia of colon with hemorrhage                                                     |
| K56.60 | Unspecified intestinal obstruction                                                          |
| K57.01 | Diverticulitis of small intestine with perforation and abscess with bleeding                |
| K57.11 | Diverticulosis of small intestine without perforation or abscess with bleeding              |
| K57.13 | Diverticulitis of small intestine without perforation or abscess with bleeding              |
| K57.21 | Diverticulitis of large intestine with perforation and abscess with bleeding                |

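### The printed bleeding list includes codes for bowel obstruction and microscopic hematuria, and the printed VTE outcome list counts chronic leg DVT, against the plan's own targets and rules

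*Combined protocol and SAP*

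**What the plan says.** **Bleeding.** Section 6.3.1 names major bleeding as the safety outcome and sends definitions to Appendix A. Section 1.5 uses it as the assay-sensitivity endpoint, with a trial ratio of 0.31 (0.17 to 0.55). Appendix A prints one general bleeding list, the Major Bleeding sheet. The only explicit reference to it is in the overt-major-bleeding exclusion: "See 'Major Bleeding' sheet for codes". The ICD-10 half of that sheet contains K56.60, "Unspecified intestinal obstruction"; R31.1, "Benign essential microscopic hematuria"; and R31.2, "Other microscopic hematuria". Perforation of the intestine appears in both halves (569.83 and K63.1).

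**VTE.** Section 1.3 gives the target as symptomatic, recurrent VTE or VTE-related death. Section 6.3.1 makes the non-fatal component operational as "Hospital admission for VTE (principal diagnosis position", and the VTE sheet is headed inpatient, primary position. That sheet includes chronic leg DVT under 453.5x and I82.5x.

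No passage justifies these codes or says that they are dropped when events are counted.

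**The concern.** A code that does not represent the target event adds false positives. If these are about equally frequent in both arms, both ratios move toward 1. For bleeding, this weakens the contrast that the assay-sensitivity check depends on. For VTE, it makes the 1.8 non-inferiority margin easier to meet when apixaban is truly worse.

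Chronic leg codes have an obvious possible source here. About 51% of matched patients in each arm already carry a DVT code at baseline (Appendix B, matched table: 1,838 and 1,836 of 3,570). A later admission coded as chronic leg DVT could reflect the index clot and not a recurrence.

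The bleeding codes also affect eligibility, because the same sheet drives an exclusion.

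**Working it through.** **1. Bleeding codes against the plan's own rules**

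- *Hematuria.* The gross-hematuria exclusion in Appendix A is limited to 599.71 (the wider 599.7x is expressly ruled out) and R31.0. The overt-major-bleeding exclusion uses the same window (one day before through drug initiation) and the same care settings, but its sheet admits R31.1 and R31.2. A patient whom the first rule keeps is therefore removed by the second.
- *Obstruction.* The gastrointestinal-bleeding exclusion runs "K28.6x, K55.21, K57.xx, K62.5x", with no K56 code. In the ICD-9 half of the Major Bleeding sheet, obstruction occurs only as a qualifier of a bleeding ulcer, for example "ACUTE GASTRIC ULCER WITH HEMORRHAGE WITH OBSTRUCTION". K56.60 has no stand-alone ICD-9 counterpart.
- *Perforation.* 569.83 and K63.1 name no bleeding either.

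**2. VTE rows by site (printed ICD-10 list)**

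- Leg, acute (I82.4x): 41 rows.
- Leg, chronic (I82.5x): 41 rows.
- Upper extremity, axillary, subclavian and jugular (I82.6x, A1x, B1x, C1x): 26 acute rows, no chronic row.
- ICD-9 shows the same split: 453.5x is chronic leg, while 453.82 to 453.87 are all acute.

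So the list follows two different rules, depending on the site.

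**3. The plan's power figure**

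Inputs from Section 10, pooled: 7,140 matched patients, risk 13.74 per 1,000, hazard ratio 0.84, margin 1.8, two-sided alpha 0.05.

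- Events: 7,140 × 13.74/1,000 = 98.1036.
- Power = Φ(ln(1.8/0.84) × √98.1036/2 − 1.96) = 0.9652, which matches the stated 0.965194245. This figure is not in dispute.

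**4. Illustration of dilution**

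Assumptions, not in the documents: f is the false-positive share of warfarin-arm events, and k is the apixaban/warfarin ratio of false positives. The observed ratio is RR × (1 − f) + k × f. One-sided error at a true hazard ratio of 1.8, with total events held at 98.1, is Φ(ln(1.8/HRobs) × √98.1036/2 − 1.96).

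With k = 1:

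| f | Bleeding, true 0.31 | VTE, true 0.84 | VTE, true 1.8 | Error at 1.8 |
|---|---|---|---|---|
| 0 | 0.31 | 0.84 | 1.80 | 2.5% |
| 5% | 0.34 | 0.85 | 1.76 | 3.2% |
| 10% | 0.38 | 0.86 | 1.72 | 4.1% |
| 20% | 0.45 | 0.87 | 1.64 | 6.7% |

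Direction depends on k. With k = 0.5 and f = 20%, VTE reads 0.84 × 0.8 + 0.5 × 0.2 = 0.77, away from 1, and bleeding reads 0.31 × 0.8 + 0.1 = 0.35. Bleeding moves up for any k above 0.31. At a true hazard ratio of 1.8, the margin is easier to meet for any k below 1.8.

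**The case against.** Several objections have weight.

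- *Labels.* A reader might infer that all three code groups are off-target by their own labels. Only K56.60 (and, on review, perforation) names no bleeding. Microscopic hematuria is bleeding, so the mismatch is with major or overt. Chronic leg DVT is VTE, so the mismatch is with the recurrent endpoint of Section 1.3 and not with the bare term in Section 6.3.1.
- *Which list defines the outcome.* Use of the Major Bleeding sheet for the safety outcome is inferred; its only explicit citation is for an exclusion. This stands, and the missing link itself needs repair.
- *Incomplete printout.* Appendix A defers to an external folder for full ICD-10 lists and missing information. A reader might infer that the bleeding definition truly differs between coding systems, since hematuria and respiratory codes appear only in the ICD-10 half. A reader might also infer that care setting is undefined, since only R31.9 carries one ("Heaturia, unspecified in inpatient confinement"). The documents do not support either conclusion, because the external file may settle both. They do not explain away codes that are actually printed.
- *Imperfect benchmark.* The gastrointestinal-bleeding exclusion itself includes K63.1x, so it is not a clean standard. K56.60 still fails on its own label.
- *Principal position.* The inpatient principal-diagnosis rule reduces chronic-code capture by an unknown amount. It does not remove it.
- *Order of analyses.* Acute-only as the primary definition is a choice between specificity and sensitivity. Keeping the present list as primary with a pre-specified acute-only analysis would also answer the point.

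**Conclusion.** The point holds for the printed lists. K56.60, R31.1 and R31.2 do not belong on a list of major or overt bleeding, and the VTE list applies no single acute/chronic rule. The plan draws the opposite line itself for hematuria and for veins outside the leg, so this is an inconsistency in stated lists and not a matter of taste.

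The size of the effect is unknown. Neither f nor k is in the documents, so every figure in the dilution table is conditional. The 41 chronic rows are a share of codes; reading them as a share of events would be unsupported. On the assumptions shown, the VTE point estimate barely moves (0.84 to 0.86 at 10%). The larger consequences would be for the bleeding check and for error at the margin. The documents set no pass/fail rule for the bleeding ratio, so no threshold of failure can be claimed. The correction is worth making because the defect can be verified and the change is cheap at this stage.

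**What to change.** Before the comparative analysis:

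1. Remove K56.60, R31.1 and R31.2 from the bleeding list, and review 569.83 and K63.1 in the same edit. Name the list that defines the bleeding outcome, and say whether the overt-major-bleeding exclusion uses the edited list.
2. Apply one acute/chronic rule across the VTE list. Either restrict the primary outcome to acute codes, as already done for other sites, or keep the present list and pre-specify the analysis without 453.5x and I82.5x. Report both.
3. Check the edits against the external code file, including whether hematuria and respiratory codes, care setting and diagnosis position agree across ICD-9 and ICD-10. Update the event rate and power if the primary VTE list changes.

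**Cost.** A code-list edit and one extra run; Section 13 is still blank. If chronic codes are dropped from the primary outcome and 10% or 20% of VTE events are lost, the rate falls from 13.74 to 12.4 or 11.0 per 1,000. Events become 88.29 or 78.48, and pooled power about 94.7% or 92.2% by the formula in step 3 of the working. If the exclusion is edited too, at most 57 + 33 + 111 = 201 patients could re-enter at that flowchart step. That step combines seven exclusions, against a final cohort of 4,264 + 6,338 + 8,400 = 19,002.
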